#### **10.10.** Follow-up

#### 10.10.1. Post-IMRT OM Follow-up

All subjects will be evaluated at  $7 \pm 2$  calendar days from the last day of IMRT (Post-IMRT Week 1) and at  $14 \pm 2$  calendar days from the last day of IMRT (Post-IMRT Week 2).

At each visit, the following should be completed:

Conduct OM assessment and record the severity using the WHO score

Record AEs and changes to concomitant medications through 30 days following the last dose of IMRT, cisplatin, or GC4419/Placebo (i.e., whichever occurs last).

Galera Therapeutics, Inc.

Version: Amendment 4

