#### 4.3. Study Period Definitions

**Study Treatment Period:** the period of time from Study Day 1 (IMRT Day 1/Baseline) through the last day of IMRT. Subjects who receive at least 60 Gy of IMRT will be considered to have completed the Study Treatment Period.

**OM** (**Oral Mucositis**) **Observation Period:** the period of time from Study Day 1 (IMRT Day 1/Baseline) through the last OM assessment. By protocol, the last OM assessment is to occur during the second week after completion of IMRT.

**AE** (Adverse Event) Observation Period: the period of time from the date of randomization through 30 days post last day of cisplatin, IMRT, or GC4419/Placebo (i.e., whichever occurs last).

**LTFU** (**Long-term Follow-up**) **Observation Period:** the period of time from last day of IMRT through 24 months post-IMRT.

Galera Therapeutics, Inc.

Version: Amendment 4

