# 10.10.2. Long-term Follow-up

All subjects will be followed for one year post-IMRT for tumor recurrence/progression. Subjects will be seen every 3 months (Months 3, 6, 9, and 12 post-IMRT)  $\pm$  30 days for each visit. At each of these visits the subject should be seen by a Radiation Oncologist, Medical Oncologist, ENT, or Head & Neck Surgeon and the following assessment should be conducted:

Clinical tumor assessment (See Section 10.6.1)

Note: a laryngopharyngoscopy is required at Months 3, 6, 9, and 12 post-IMRT. However, if local/regional progression or recurrence has already been discovered at a previous visit, a laryngopharyngoscopy is no longer required at future visits. If distant progression is discovered at a previous visit, a laryngopharyngoscopy is still required at subsequent visits to assess the subject for local/regional progression/recurrence. A head/neck/oral exam must always be conducted at Months 3, 6, 9, and 12 post-IMRT.

Survival status assessment (See Section 10.6.3)

Radiographic imaging must be performed at Month 12 post-IMRT for all subjects. Subjects treated definitively (as opposed to post-operatively) will also undergo imaging at Month 3 post-IMRT to assess tumor response/clearance to the degree possible.

As indicated in Section 10.6.2.2, radiographic imaging is highly recommended if disease progression is suspected by the treating physician at any of the above time points. If radiographic imaging is performed, both local/regional recurrence and distant metastases should be evaluated. Biopsy of any lesion(s) suspicious for tumor recurrence is also recommended.

When possible, the same imaging technique (i.e., CAT, PET, or MRI) that was used for pretreatment tumor imaging at the time of staging should be used for post-treatment tumor imaging.

The following assessments must also be conducted at 3, 6, 9, and 12 months post-IMRT:

BUN and creatinine assessment

Weight assessment

Subjects will continue to be followed for survival only for two years post-IMRT at 16, 20 and 24 months (see section 10.6.3).

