# 11.2.2. All Adverse Events (AEs) Regardless of Seriousness

Any adverse medical condition or laboratory abnormality with an onset date before the date of randomization is considered to be pre-existing in nature, and part of a subject's medical history. Adverse medical conditions that begin on or after date of randomization will be considered an adverse event, including SAEs, and followed for 30 days after the last dose of IMRT, cisplatin, or GC4419/Placebo (i.e., whichever occurs last), hereafter referred to as the "30 Day Follow-up Period". Similarly, new events will be reported as AEs/SAEs if the start date is within 30 Day Follow-up Period. Increases in toxicity grade of pre-existing conditions that occur on or after the date of randomization are also considered an adverse event.

All adverse events must be recorded in the subject's source documents and on the CRF regardless of frequency, severity (grade) or assessed relationship to randomized therapy.

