### APPENDIX 1. SCHEDULE OF ASSESSMENTS

**Table 6: Schedule of Assessments** 

Assessments	Screening	Treatment						Follow-up						
					Post-IMRT	Long-term Follow-up								
											OM Follow-up			
	≤28 days	Wk 1		Wk 2	Wk 3	Wk 4	Wk 5	Wk 6	Wk 7	Last Day	Post-IMRT	Months 3,	Months	Months 16, 20,
	of IMRT Day 1	Baseline (IMRT Day 1)	Days 2-7	Days 8-14	Days 15-21	Days 22-28	Days 29-35	Days 36-42	Days 43-49	of IMRT or Early Term 	Wks 1 & 2 (±2 D) 	6, 9, & 12 Post- IMRT (±30 D)	3 & 12 Post- IMRT (±30 D)	24 Post-IMRT (±30 D)
Informed consent	X													
Inclusion/exclusion criteria 	X	X												
Dental exam/IMRT clearance	X													
Medical and HNC histories 	X													
Record tobacco use	X	X		X	X	X	X	X	X					
Complete physical exam 	X									X				
Height	X													
Weight	X	X		X	X	X	X	X	X	X				
Symptom-directed PE						X								
Vital signs, ECOG 	X	X				X			X	X				
Record BSA 		X		X	X	X	X	X	X					
Tumor imaging 	X												X	
Clinical tumor assessment 										X		X	X	
Concomitant medications 	X	X	Weeko	days						X	X			
Adverse Events 	X	X	Weeko	days						X	X			
ECG (12-lead) 	X													
OM assessment 	X	X	X	Twice-	weekly				X	X	X			
Blood draw: Serum pregnancy test 	X													
Blood draw: Lab safety tests 	X	X	X	X	X	X	X	X	X	X 				
Blood draw: Serum cotinine 		X				X				X				
Blood draw: PK 		X	X			X								
Blood draw: Cytokines 	X	X		X		X		X		X				
Blood draw: RNA 	X									X				
Dosing GC4419/Placebo 		X Weekdays when IMRT is given X												
BUN, creatinine, and weight								X						
Survival Status 			1									X	X	X

BSA = body surface area; ECG = electrocardiogram; ECOG = Eastern Cooperative Oncology Group; HNC = head and neck cancer, IMRT = intensity-modulated radiation therapy; OM = oral mucositis; PE = physical examination; PK = pharmacokinetics

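### AEs are reportable to 30 days after the last treatment, but the last visit that lists AE recording is about Day 14, so the final 14–18 days of that window have no scheduled AE contact

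*Combined protocol and SAP*

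**What the plan says.** **The window.** Section 4.3 defines the AE Observation Period as "the period of time from the date of randomization through 30 days post last day of cisplatin, IMRT, or GC4419/Placebo", whichever comes last. The safety endpoint in Section 5.2 covers how often AEs and SAEs occur, how long they last and how severe they are within that period. Section 11.2.2 adds that "new events will be reported as AEs/SAEs if the start date is within 30 Day Follow-up Period". Section 11.5 and footnote 11 to Table 6 give the same 30-day limit. Section 8.9 and footnote 10 apply it to concomitant medications.

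**The visits.** Section 10.10.1 schedules two visits after IMRT, at 7 ± 2 and 14 ± 2 days, and lists for each of them the instruction to "Record AEs and changes to concomitant medications through 30 days following the last dose of IMRT, cisplatin, or GC4419/Placebo". In Table 6 the "Adverse Events" and concomitant-medication rows are last marked at these two visits.

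**What follows.** The next visit is Month 3 ± 30 days. Section 10.10.2 lists a clinical tumor assessment, survival status and, for definitively treated subjects, imaging. It then states "The following assessments must also be conducted at 3, 6, 9, and 12 months post-IMRT", and the items named are BUN/creatinine and weight. Neither the text nor Table 6 has an AE or medication item at that visit. No Day 30 visit or call appears in the text, the table or its footnotes.

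**The concern.** A site that follows the schedule exactly has no planned occasion to ask about AEs in the second half of the post-treatment window. The instruction to record through Day 30 cannot be completed at the visits that carry it.

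Three parts of the safety evaluation are exposed:

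- **Incidence.** Events that start after the Week 2 visit reach the database only if the subject volunteers them or the site finds them in the chart or at an unscheduled contact.
- **Duration and status.** Section 11.5 classes non-serious AEs as ongoing if they are unresolved 30 days after the last study drug dose. When study drug runs to the end of IMRT, no scheduled contact establishes status on that date.
- **Laboratory events.** The scheduled chemistry and hematology profiles end with the last day of IMRT (Section 10.1.2; Table 6, footnote 15).

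This matters because Appendix 8 gives the safety database for the marketing application as one reason for raising enrollment to 450.

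**Working it through.** The plan gives no coverage figure to reproduce. The check is calendar arithmetic on its own definitions.

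**Inputs**

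- Length of the post-treatment window: 30 days after the last of the three treatments (Section 4.3).
- Last visit that lists AE recording: day *v* after IMRT, with *v* = 12 to 16 (Section 10.10.1).
- Delay from the last IMRT fraction to the last cisplatin dose: *x* days. *x* = 0 means that IMRT is last. The documents give no distribution for *x*, so 3 and 7 are assumed for illustration.
- Example calendar: IMRT ends on Day 47 and the last cisplatin dose is on Day 43 (Table 3).

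**1. Uncovered days**

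The visits are tied to IMRT and the window to the last treatment, so

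uncovered days = 30 + *x* − *v*; share of tail = (30 + *x* − *v*) / 30.

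| | *v* = 16 | *v* = 14 | *v* = 12 |
|---|---|---|---|
| *x* = 0 (IMRT last) | 14 days (47%) | 16 days (53%) | 18 days (60%) |
| *x* = 3 (assumed) | 17 days (57%) | 19 days (63%) | 21 days (70%) |
| *x* = 7 (assumed) | 21 days (70%) | 23 days (77%) | 25 days (83%) |

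In the Table 3 example cisplatin ends before IMRT, so the first row applies. The other rows are possible because Section 6.2 lets cisplatin timing vary and Section 9.1 lets its schedule be altered for toxicity.

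**2. Share of the whole AE Observation Period**

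In the Table 3 example, Day 1 to the end of the window is 47 + 30 = 77 days. The uncovered part is 14/77 = 18% to 18/77 = 23%. The period starts at randomization, before Day 1, so the true share is somewhat lower. AEs are recorded on all IMRT days, so coverage before the tail is dense.

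**3. Distance to the next visit**

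Three months is about 91 days, so Month 3 ± 30 days runs from about Day 61 to Day 121. With IMRT last, that is 61 − 30 = 31 to 121 − 30 = 91 days after the window closes.

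**4. After the fix**

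A scheduled contact on or just after Day 30 from the last treatment reduces the uncovered part from 14–18 days to 0.

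**The case against.** The strongest reply is that the plan omits a named contact, not the duty to collect. Much of this stands.

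- **Reporting is defined by onset date.** Footnote 11 to Table 6 and Section 11.2.2 require an event that starts on Day 25 to be recorded whenever the site learns of it, and Section 11 makes the investigator responsible for detecting events. A reader might infer that half of the post-treatment window is simply not ascertained. The documents do not support that.
- **Month 3 is not empty.** Section 10.6.1, to which Section 10.10.2 refers, requires a short history and a physical examination by a specialist. Section 11.4 counts history, examination, laboratory results and verbal reports among the sources of AEs, so some late events may surface. But no line asks for AEs there, and recall would be a month or more past the window when IMRT is last.
- **Section 11.5 asks for proactive follow-up.** This applies once an AE or SAE has been reported. It helps with outcome and duration but does not find new events.
- **Both arms have the same schedule under blinding.** A reader might infer a between-arm bias, and nothing in the documents shows one. Equal under-capture would still lower the counts in both arms and shrink absolute differences, which is the less cautious direction for a safety comparison.
- **Other materials may cover it.** Section 11.2.1 places SAE reporting instructions in a separate manual, which is not available here. If it or the CRF guidelines schedule a Day 30 contact, a cross-reference would suffice.

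**Conclusion.** The gap is real and of moderate size. With IMRT as the last treatment, the final 14–18 of the 30 post-treatment days (47–60% of the tail) have no scheduled AE contact. The percentage refers to the tail only; on the Table 3 calendar it is about 18–23% of the time from Day 1. The gap lengthens day for day if cisplatin ends after IMRT, but the documents do not say how often that happens.

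Late AE incidence, duration and Day 30 status may therefore be under-captured, probably similarly in both arms. It would be tempting to say that AE incidence will be underestimated. The documents give neither a late-event rate nor a capture rate, so neither the certainty nor the amount can be established. The conclusion assumes that no document outside those available schedules a contact near Day 30.

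This goes beyond missing detail, because full compliance with the schedule still leaves late events to passive reporting. It does not affect the efficacy analyses.

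**What to change.** **Preferred.** Add to Section 10.10 and Table 6 one telephone contact at about Day 30 after the last of IMRT, cisplatin or GC4419/Placebo, to collect AEs, SAEs and concomitant medications and to update the status of open events. Tie it to the last of the three treatments rather than to IMRT, and set its window on or after Day 30 (for example Day 30 to 37) so that no part of the tail is left out.

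**Minimum.** Add a line to Section 10.10.2 and the Month 3 column of Table 6 for AEs, SAEs and concomitant medications, limited to AE onset or medication use through Day 30. This uses an existing visit but relies on recall 31 to 91 days after the window closes when IMRT is last.

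**Cost.** One call per subject (at most about 450 at planned enrollment, and fewer if added after enrollment has begun), or a few minutes at Month 3. Either needs a protocol amendment with IRB/IEC/REB approval (Sections 13.2 and 14.4) across approximately 100 sites, so it is best combined with another amendment. AE counts may rise slightly. If a manual already schedules such a contact, citing it in Section 10.10 and Table 6 is enough.

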# 10.10.2. Long-term Follow-up

All subjects will be followed for one year post-IMRT for tumor recurrence/progression. Subjects will be seen every 3 months (Months 3, 6, 9, and 12 post-IMRT)  $\pm$  30 days for each visit. At each of these visits the subject should be seen by a Radiation Oncologist, Medical Oncologist, ENT, or Head & Neck Surgeon and the following assessment should be conducted:

Clinical tumor assessment (See Section 10.6.1)

Note: a laryngopharyngoscopy is required at Months 3, 6, 9, and 12 post-IMRT. However, if local/regional progression or recurrence has already been discovered at a previous visit, a laryngopharyngoscopy is no longer required at future visits. If distant progression is discovered at a previous visit, a laryngopharyngoscopy is still required at subsequent visits to assess the subject for local/regional progression/recurrence. A head/neck/oral exam must always be conducted at Months 3, 6, 9, and 12 post-IMRT.

Survival status assessment (See Section 10.6.3)

Radiographic imaging must be performed at Month 12 post-IMRT for all subjects. Subjects treated definitively (as opposed to post-operatively) will also undergo imaging at Month 3 post-IMRT to assess tumor response/clearance to the degree possible.

As indicated in Section 10.6.2.2, radiographic imaging is highly recommended if disease progression is suspected by the treating physician at any of the above time points. If radiographic imaging is performed, both local/regional recurrence and distant metastases should be evaluated. Biopsy of any lesion(s) suspicious for tumor recurrence is also recommended.

When possible, the same imaging technique (i.e., CAT, PET, or MRI) that was used for pretreatment tumor imaging at the time of staging should be used for post-treatment tumor imaging.

The following assessments must also be conducted at 3, 6, 9, and 12 months post-IMRT:

BUN and creatinine assessment

Weight assessment

Subjects will continue to be followed for survival only for two years post-IMRT at 16, 20 and 24 months (see section 10.6.3).

## 11. ADVERSE EVENTS AND SERIOUS ADVERSE EVENTS

The Investigator is responsible for the detection and documentation of events meeting the criteria and definition of an AE or SAE as provided in this protocol. Throughout the study, AEs will be recorded in the source documents and on the appropriate pages of the CRF regardless of whether the AEs are considered related to GC4419/Placebo. To avoid confusion, the AE should be recorded in standard medical terminology.

#### 11.1. Definitions

The following definitions of terms are guided by the ICH and the US CFR and are included here verbatim.

Galera Therapeutics, Inc.

Version: Amendment 4

# 11.1.1. Adverse Event (AE)

An AE is any untoward medical occurrence in a patient or clinical investigation subject administered a pharmaceutical product and which does not necessarily have a causal relationship with this treatment. An AE can therefore be any unfavorable and unintended sign (including an abnormal laboratory finding), symptom, or disease temporally associated with the use of a medicinal (investigational) product, whether or not related to the medicinal (investigational) product.

Examples of an AE include:

Significant or unexpected worsening or exacerbation of the condition/indication under study.

Exacerbation of a chronic or intermittent pre-existing condition including either an increase in frequency and/or intensity (grade) of the condition.

New conditions detected or diagnosed after investigational product administration even though they may have been present prior to the start of the study.

Signs, symptoms, or the clinical sequelae associated with a suspected interaction of the investigational product with a concomitant medication.

Signs, symptoms, or the clinical sequelae associated with a suspected overdose of either investigational product or a concurrent medication.

#### 11.1.2. Serious Adverse Event (SAE)

Any untoward medical occurrence that at any dose:

Results in death,

Is life-threatening

Note: The term 'life-threatening' in the definition of 'serious' refers to any adverse drug experience [adverse event] that places the patient or subject, in the view of the Investigator, at immediate risk of death from the reaction as it occurred, i.e., it does not include a reaction that, had it occurred in a more severe form, might have caused death. [emphasis added]

Requires inpatient hospitalization or prolongation of hospitalization

Note: In general, hospitalization signifies that the patient or subject has been detained (usually involving at least an overnight stay) at the hospital or emergency ward for observation and/or treatment that would not have been appropriate in the physician's office or outpatient setting. Complications that occur during hospitalization are AEs. If a complication prolongs hospitalization or fulfills any other serious criteria, the event is serious. When in doubt as to whether "hospitalization" occurred or was necessary, the AE should be considered serious. Hospitalization for elective treatment of a pre-existing condition that did not worsen from baseline is not considered an AE.

Results in persistent or significant disability/incapacity

Note: The term disability means a substantial disruption of a person's ability to conduct normal life functions.

Galera Therapeutics, Inc.

Version: Amendment 4

OR

Is a congenital abnormality/birth defect.

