#### **8.9.1.** Prohibited Medications

Investigators may prescribe any concomitant medication or supportive therapy deemed necessary to provide adequate supportive care including antiemetics, systemic antibiotics, hydration to prevent renal damage, topical fluoride etc., with the following exceptions:

Galera Therapeutics, Inc.

Version: Amendment 4

Low-level laser treatment for OM

Amifostine (Ethyol®)

Benzydamine (Difflam®, Pharixia®, Tantum Verde)

Cetuximab (Erbitux®)

Glutamine in any form

GM-CSF applied topically

'Magic mouthwashes' or 'Miracle mouthwashes' are permitted, provided they do not contain:

- Chlorhexidine
- Hydrogen peroxide
- Diphenhydramine (Benadryl®) liquid formulation
- Tetracycline
- Any other listed disallowed medications
- Notes:
  - Topical lidocaine preparations are permitted
  - o Diphenhydramine (Benadryl®) administered as tablets or by injection is permitted

MuGardTM, Gelclair®, Episil®, or other barrier devices

Caphosol®

Nitrates, phosphodiesterase type 5 (PDE 5) inhibitors (e.g., sildenafil, tadalafil, or similar agents) or other drugs that in the judgment of the treating Investigator could create a risk of a precipitous decrease in blood pressure are prohibited until at least 24 hours after the last dose of GC4419

Pyridostigmine or other drugs that in the judgment of the treating Investigator could create a risk of increased carotid sinus sensitivity, symptomatic bradycardia, or syncopal episodes are prohibited until at least 24 hours after the last dose of GC4419

Palifermin (Kepivance®) or other keratinocyte or fibroblast growth factor

Povidone-iodine rinses

Steroid rinses

Sucralfate in suspension form (use of sucralfate tablets is permitted)

Other biologic response modifiers – except systemic hematopoietic growth factors for the management of anemia or myelosuppression

Galera Therapeutics, Inc.

Version: Amendment 4

Concurrent approved or investigational anti-cancer therapy (e.g., chemotherapy, immunotherapy, targeted therapy, hormone and biologic therapy) other than the Protocol regimen

Other investigational agents or perceived herbal/homeopathic or other remedies for OM, which are considered investigational for purposes of this study (includes nitric oxide)

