# 11.5. Follow-up of AEs and SAEs

If an adverse event changes in grade within the date of randomization through the 30 Day Reporting Period, the event should be recorded as a new AE.

After the initial AE/SAE report, the Investigator is required to proactively follow each subject and provide further information on the subject's condition. The Investigator will ensure that follow-up includes any supplemental investigations as may be indicated to elucidate the nature and/or causality of the AE or SAE. This may include additional laboratory tests or investigations, histopathological examinations, or consultation with other health care professionals.

Non-serious AEs that have not resolved within 30 days after last dose of GC4419/Placebo will be considered ongoing, and marked as such in the CRF. All SAEs will be followed until they resolve or a new baseline is established, at which point the appropriate CRF page(s) or SAE Report Form(s) will be updated.

Routine collection of AEs will stop 30 days after last dose of GC4419/Placebo, IMRT, or cisplatin (i.e., whichever occurs last); however, collection of clinical data will continue on AEs of interest or as clinical circumstances warrant that exceed the 30 days after last dose of GC4419/Placebo, per below and described in other sections of the Protocol:

- OM: 2 weeks post last IMRT dose (Section 10.10.1)
- Medical events, which in the opinion of the Investigator, serious and are believed to be a result of study participation to warrant notifying the Sponsor (Sections 11.6 and 11.8). In these circumstances, the Investigator should contact the Galera Medical Monitor (or designee) directly to discuss the case, and how it should be reported.

As reasonably requested by the Sponsor, the Investigator will perform or arrange for the conduct of supplemental measurements and/or evaluations to elucidate as fully as possible the nature and/or causality of the AE or SAE. If a subject dies during participation in the study or during a recognized follow-up period, the Sponsor will be provided with a copy of any post-mortem findings, including histopathology.

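### The SAE definition has no criterion for a medically important event, so some infusion reactions clearly managed as outpatient events need not be reported within 24 hours

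*Combined protocol and SAP*

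**What the plan says.** Section 11.1.2 lists five grounds for calling an event serious:

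1. Death: "Results in death".
2. Life-threatening. The Investigator's view decides, but only on immediate risk of death from the event as it happened; "it does not include a reaction that, had it occurred in a more severe form, might have caused death".
3. Hospital stay: "Requires inpatient hospitalization or prolongation of hospitalization". A note extends this to detention at a hospital or emergency ward for observation or "treatment that would not have been appropriate in the physician's office or outpatient setting". It also says that doubt about whether hospitalization took place or was needed is resolved towards serious.
4. Lasting or marked disability.
5. "Is a congenital abnormality/birth defect".

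Section 11.2.1 requires sites to report events meeting these criteria within 24 hours of learning of them, and asks for the seriousness criterion in the initial report. Sections 11.2.2 and 11.4 send all AEs to the CRF, and give no expedited timeline for non-serious ones.

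The protocol treats acute haemodynamic events as a recognised risk. Exclusion criteria 15 and 16 in Section 7.2 concern precipitous falls in blood pressure, bradycardia and syncope. Section 8.9.1 restricts drugs that "could create a risk of increased carotid sinus sensitivity, symptomatic bradycardia, or syncopal episodes are prohibited until at least 24 hours" after the last dose. Section 9.1 has a rule triggered by hypotension of Grade 2 or above within two hours of the start of an infusion.

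**The concern.** The reactions that the protocol guards against are ones that can be treated in the infusion area and resolve during the same visit. Such an event may be clinically important and may have needed intervention to stop it getting worse, yet meet none of the five outcomes. An Investigator who wants to escalate it has no listed criterion to cite, although Section 11.2.1 asks for one.

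Seriousness decides several things in this protocol:

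- the 24-hour report to the Sponsor and the written notice of serious events to the ethics board (Section 11.2.1);
- the safety reports to investigators, which cover unexpected, serious, drug-related events (Section 11.7);
- follow-up until resolution or a new baseline, where an unresolved non-serious AE is simply marked ongoing (Section 11.5);
- entry in the SAE tabulation and the detailed SAE listing (Section 12.4).

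Scheduled haemodynamic monitoring around infusions is limited. Section 10.1.1 requires blood pressure before and after infusion on Days 1 and 22 only, and the schedule of assessments places the ECG at screening only. On most infusion days, AE reporting is therefore the main way in which such a reaction reaches the Sponsor, so its speed matters.

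**Working it through.** The plan gives no figure on this point and no arithmetic applies. The check has two parts: run a defined case through the five criteria, then look for any other route to serious status or 24-hour reporting.

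**The case (an assumption, not a reported event).** A subject has syncope with symptomatic bradycardia during or shortly after infusion. It is treated on site and resolves. The Investigator sees no immediate risk of death. The subject is not held at a hospital or emergency ward, and nobody doubts that hospitalization was unnecessary.

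| Criterion in 11.1.2 | Met? | Reason |
|---|---|---|
| Death | No | Subject recovered |
| Life-threatening | No | No immediate risk as it occurred; what a worse episode might have done is expressly set aside |
| Hospitalization | No | Care was suited to an outpatient setting; no doubt for the doubt rule to resolve |
| Disability | No | Resolved |
| Congenital defect | No | Not applicable |

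**Other routes examined.**

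- *Section 11.5.* It speaks of "Medical events, which in the opinion of the Investigator, serious and are believed to be a result of study participation". This concerns data collected beyond the 30-day window. It takes the event to be serious already, requires attribution to study participation, and sets no 24-hour limit.
- *Table 5 (Section 11.2.5).* Medical significance appears in the Grade 3 row. That grades severity and does not define seriousness.
- *Section 11.3.* It treats possibly related events as related for expedited reporting. That settles causality, not seriousness.
- *Section 11.7.* It gives the Sponsor the final decision on regulatory reporting, but does not make a site report a non-serious AE sooner.
- *Section 11.2.1.* It refers to a separate manual for SAE reporting instructions. Nothing says that the manual widens the definition.

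**Result.** Seriousness criteria: 5. Criteria for a medically important event: 0. Other 24-hour reporting routes found: 0. The case is a non-serious AE with no 24-hour requirement.

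**The case against.** The strongest reply is that the gap is narrow and the events remain visible. Much of this stands.

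- The life-threatening criterion already uses the Investigator's judgement. The hospitalization note reaches emergency-ward detention and resolves doubt towards serious. A reader might infer that any syncope or bradycardia treated in the infusion area escapes 24-hour reporting. The documents do not support that: only events clear of all these provisions do, and for them a 24-hour report is not required rather than forbidden.
- All AEs go on the CRF with grade, relationship and the action taken with study drug (Section 11.4). Section 12.4 tabulates treatment-emergent, severe and treatment-related AEs and lists withdrawals due to AEs. The DMC makes periodic unblinded safety reviews (Sections 12.9 and 13.4) that are not described as limited to SAEs.
- Section 11.7 commits the Sponsor to reporting AEs under the applicable regulation, so its assessment is not expressly confined to the site's five-item check. The loss is mainly time, since the Sponsor may first see the event on the CRF.
- A reader might infer a biased SAE comparison between arms. The SAE tables would omit these events, but the tables are descriptive, the same definition applies to both blinded arms, and the events still appear in the AE tables.
- A reader might try to size the problem by multiplying subjects by infusions. That gives maximum exposure, not affected events.
- Section 11.1 says of its definitions: "The following definitions of terms are guided by the ICH and the US CFR and are included here verbatim". A reader might infer that an item was dropped from a source text. Those sources are not in the documents, so the point does not rest on that sentence.

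None of this supplies the missing criterion. CRF recording and DMC review do not replace a 24-hour report.

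**Conclusion.** The point holds in a limited form. Section 11.1.2 has no criterion for a medically important event, and Section 11.2.1 hangs 24-hour reporting on that list. Infusion-related syncope, symptomatic bradycardia or hypotension clearly managed as an outpatient, with no immediate risk of death and no doubt about hospitalization, is not required to be reported within 24 hours and is not tabulated as an SAE.

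The size cannot be calculated, because the documents give no rate for such events. The conclusion assumes that the unseen SAE manual does not add a criterion. It does not touch the primary efficacy analysis. This is a change that should be made: a site following the list as written would classify these events as non-serious.

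**What to change.** Add a sixth criterion to Section 11.1.2: an event that the Investigator judges medically important because it may jeopardize the subject, or because it needs intervention to prevent one of the listed outcomes. Name infusion-related syncope, symptomatic bradycardia and hypotension needing intervention as examples to consider, not as automatic SAEs. Put the same text in the SAE manual. This alters reporting only and leaves every dosing and treatment rule as it is.

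Apply it prospectively. Optionally, make one review, blinded to arm, of already recorded AEs of these types before database lock.

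The prospective change costs an amendment to the protocol and manual and somewhat more SAE reports for sites and Sponsor. The optional review costs more: enrollment began in October 2018, so it would bring late SAE forms, causality and ethics-board follow-up, and safety-database reconciliation. Section 8.2.1 lets Sponsor or CRO staff unblind a subject once an SAE is reported, so late reports should be handled in a way that protects the blind.
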